6.21.5. Definitions of Tumor Response and Progression

Responses will be categorized as CR, PR, SD, or PD. In addition, a response category of not evaluable (NE) is provided for situations in which there is inadequate information to otherwise categorize response status. A response category of no disease (ND) is included for situations in which there is no evidence of tumor either at baseline or on treatment.

The best overall response will be determined. The best overall response is the best response recorded from the start of treatment until progressive disease/recurrence (taking as reference for PD the smallest measurements recorded since treatment started). Subjects with NE or ND will be included in the denominator in the analyses of tumor response rates

6.21.5.1. Complete Response

To satisfy criteria for a CR, all of the following criteria must be met:

- No evidence of new disease
- Absolute Lymphocyte Count (ALC) in peripheral blood of $< 4 \times 10^9/L$
- Regression of all index nodal masses to normal size (≤ 1.5 cm in the LD)
- Normal spleen and liver size
- Regression to normal of all nodal non-index disease and disappearance of all detectable non-nodal, non-index disease
- Morphologically negative bone marrow defined as $< 30\%$ of nucleated cells being lymphoid cells and no lymphoid nodules in a bone marrow sample that is normocellular for age
- Peripheral blood counts meeting all of the following criteria:
 - ANC $> 1.5 \times 10^9/L$ without need for exogenous growth factors (eg, G-CSF)
 - Platelet count $\geq 100 \times 10^9/L$ without need for exogenous growth factors

- Hemoglobin ≥ 110 g/L (11.0 g/dL) without red blood cell transfusions or need for exogenous growth factors (eg, erythropoietin)

Note: Subjects who fulfill all the criteria for a CR (including bone marrow criteria) but who have a persistent anemia, thrombocytopenia, or neutropenia or a hypocellular bone marrow that is related to prior or ongoing drug toxicity (and not to CLL) will be considered as a CR with incomplete marrow recovery (CRI).

6.21.5.2. Partial Response

To satisfy criteria for a PR, all of the following criteria must be met:

- No evidence of new disease
- Change in disease status meeting ≥ 2 of the following criteria, with 2 exceptions in which only 1 criterion is needed: (1) Only lymphadenopathy is present at baseline; (2) Only lymphadenopathy and lymphocytosis are present at baseline. In these 2 cases, only lymphadenopathy must improve to the extent specified below:
 - In a subject with baseline lymphocytosis ($ALC \geq 4 \times 10^9/L$), a decrease in peripheral blood ALC by $\geq 50\%$ from baseline or a decrease to $< 4 \times 10^9/L$
 - A decrease by $\geq 50\%$ from the baseline in the SPD of the index nodal lesions
 - In a subject with enlargement of the spleen at baseline, a splenomegaly response as defined in Section [6.21.4.2.1](#)
 - In a subject with enlargement of the liver at baseline, a hepatomegaly response as defined in Section [6.21.4.2.2](#)
 - A decrease by $\geq 50\%$ from baseline in the CLL marrow infiltrate or in B-lymphoid nodules
- No index, splenic, liver, or non-index disease with worsening that meets the criteria for definitive PD
- Peripheral blood counts meeting ≥ 1 of the following criteria:
 - $ANC > 1.5 \times 10^9/L$ or $\geq 50\%$ increase over baseline without need for exogenous growth factors (eg, G-CSF)
 - Platelet count $\geq 100 \times 10^9/L$ or $\geq 50\%$ increase over baseline without need for exogenous growth factors
 - Hemoglobin ≥ 110 g/L (11.0 g/dL) or $\geq 50\%$ increase over baseline without red blood cell transfusions or need for exogenous growth factors (eg, erythropoietin)

6.21.5.3. Stable Disease

To satisfy criteria for SD, the following criteria must be met:

- No evidence of new disease
- There is neither sufficient evidence of tumor shrinkage to qualify for PR nor sufficient evidence of tumor growth to qualify for definitive PD

6.21.5.4. Definitive Progressive Disease

The occurrence of any of the following events indicates definitive PD:

- Evidence of any new disease:
 - A new node that measures > 1.5 cm in the LD and > 1.0 cm in the LPD
 - New or recurrent splenomegaly, with a minimum LVD of 14 cm
 - New or recurrent hepatomegaly, with a minimum LVD of 20 cm
 - Unequivocal reappearance of an extra-nodal lesion that had resolved
 - A new unequivocal extra-nodal lesion of any size
 - New non-index disease unequivocally attributable to CLL (eg, soft tissue, effusions, ascites, or other organ abnormalities related to CLL)

Note: Isolated new effusions, ascites, or other organ abnormalities are not sufficient evidence alone of PD unless histologically confirmed. Thus, a declaration of PD should not be made if this is the only manifestation of apparently new disease.

- Evidence of worsening of index lesions, spleen or liver, or non-index disease:
 - Increase from the nadir by $\geq 50\%$ in the SPD of index lesions
 - Increase from the nadir by $\geq 50\%$ in the LD if an individual node or extra-nodal mass that now has an LD of > 1.5 cm and an LPD of > 1.0 cm
 - Splenic progression, defined as an increase in splenic enlargement by $\geq 50\%$ from nadir (with a minimum 2 cm increase and a minimum LVD of 12 cm)
 - Hepatic progression, defined as an increase in hepatic enlargement by $\geq 50\%$ from nadir (with a minimum 2 cm increase and minimum LVD of 18 cm)

- Unequivocal increase in the size of non-index disease (eg, effusions, ascites, or other organ abnormalities related to CLL)
- Transformation to a more aggressive histology (eg, Richter syndrome) as established by biopsy (with the date of the biopsy being considered the date of CLL progression if the subject has no earlier objective documentation of CLL progression).
- Decrease in platelet count or hemoglobin that is attributable to CLL, is not attributable to an autoimmune phenomenon, and is confirmed by bone marrow biopsy showing an infiltrate of clonal CLL cells
 - The current platelet count is $< 100 \times 10^9/L$ and there is a decrease by $> 50\%$ from the highest on-study platelet count
 - The current hemoglobin is $< 110 \text{ g/L (11.0 g/dL)}$ and there is a decrease by $> 20 \text{ g/L (2 g/dL)}$ from the highest on-study hemoglobin

Note: If there is uncertainty regarding whether there is true progression, the subject should continue study treatment and remain under close observation (eg, evaluated at 4-week intervals) pending confirmation of progression status by the IRC. In particular, worsening of constitutional symptoms in the absence of objective evidence of worsening CLL will not be considered definitive disease progression. In such subjects, both CLL-related and non-CLL-related causes for the constitutional symptoms should be considered. Worsening of disease during temporary interruption of study treatment (eg, for intercurrent illness) is not necessarily indicative of resistance to study treatment. In these instances, CT/MRI or other relevant evaluations should be considered in order to document whether definitive disease progression has occurred. If subsequent evaluations suggest that the subject has experienced persistent definitive CLL progression, then the date of progression should be the timepoint at which progression was first objectively documented.

6.21.5.5. Non-Evaluable

In a subject who does not have evidence of PD, the occurrence of any of the following conditions indicates a response status of NE:

- There are no images or inadequate or missing images.
- Images of the liver and spleen are missing at that time point (with the exception that absence of splenic images will not result in an NE designation in a subject known to have undergone splenectomy).

Note: A time-point will be considered to have a response of NE if any index lesion is missing. PD may be assigned at any time point regardless of the extent of missing index or non-index lesions. Missing non-index lesions will not impact the ability to assess for response or disease progression.

6.21.5.6. No Disease

Subjects have a status of ND if all of the following conditions occur:

- Index disease absent at both baseline and on-treatment.
- Non-index disease absent at both baseline and on-treatment.
- Enlargement of the liver and spleen absent at both baseline and on-treatment
- Abnormalities of peripheral blood counts (elevated ALC and abnormally low ANC, platelet count, and hemoglobin) and evidence of CLL in bone marrow (if available) absent at both baseline and on treatment

6.21.6. Lymphocytosis During Therapy

GS-9973 will probably mobilize CLL cells from tissues into the peripheral blood. This characteristic pharmacological action can be prominent early in therapy but can persist over time and should not be confused with disease progression in subjects who have persistent control of other CLL-related signs and symptoms. *In the absence of other objective evidence of disease progression, the occurrence of lymphocytosis will not preclude subjects from meeting the criteria for a PR if other criteria for PR are met and will not be considered evidence of CLL progression if occurring in isolation.* Subjects with lymphocytosis should be continued on study therapy until the occurrence of definitive disease progression (ie, disease progression that is manifest by worsening CLL-related signs other than lymphocytosis alone), or the occurrence of another reason to discontinue study therapy {Cheson 2012}.

6.22. Documentation of Definitive CLL Progression

Of importance, CLL response and progression data will be subjected to IRC review (see Section 9.4). If there is uncertainty regarding whether there is definitive progression, the subject should continue study drug(s) pending confirmation of progression status by the IRC.

7. ADVERSE EVENTS AND TOXICITY MANAGEMENT

7.1. Adverse Events

An adverse event (AE) is any untoward medical occurrence in a clinical investigation subject administered a medicinal product and which does not necessarily have a causal relationship with this treatment. An AE can therefore be any unfavorable and unintended sign, symptom, or disease temporally associated with the use of a medicinal product, whether or not considered related to the medicinal product.

AEs also include the following:

- All AEs that occur from the signing of the informed consent onwards and throughout the duration of the study, including the 30-day follow-up off-study period.
- Pre- or post-treatment complications that occur as a result of a protocol-mandated procedure (eg, venipuncture or biopsy) during or after screening (before the administration of study investigational medicinal product)
- Any pre-existing condition that increases in severity, or changes in nature during or as a consequence of the study investigational medicinal product phase of this trial, will also be considered an AE
- Complications and termination of pregnancy

An AE does not include the following:

- Medical or surgical procedures (eg, surgery, endoscopy, tooth extraction, transfusion) performed; the condition that led to the procedure may be an AE if applicable
- Pre-existing diseases or conditions or laboratory abnormalities present or detected before the screening visit that do not worsen
- Situations where an untoward medical occurrence has not occurred (eg, hospitalization for elective surgery, social and/or convenience admissions)
- Overdose without clinical sequelae (see Section 7.7)
- Any medical condition or clinically significant laboratory abnormality with an onset date before the consent form is signed. It is considered to be pre-existing and should be documented on the medical history eCRF
- Uncomplicated pregnancy
- An induced elective abortion to terminate a pregnancy without medical reason

7.2. Serious Adverse Events

A **serious adverse event** (SAE) or serious adverse drug reaction (SADR) is defined as follows:

Any adverse drug experience occurring at any dose that results in any of the following outcomes:

- Death
- Life-threatening situation (subject is at immediate risk of death)
- In-patient hospitalization or prolongation of existing hospitalization
- Persistent or significant disability/incapacity
- Congenital anomaly/birth defect in the offspring of a subject who received investigational medicinal product
- Other: medically significant events that may not be immediately life-threatening or result in death or hospitalization, but based upon appropriate medical and scientific judgment, may jeopardize the subject or may require medical or surgical intervention to prevent one of the outcomes listed above

Examples of such events are as follows:

- Intensive treatment in an emergency room or at home for allergic bronchospasm
- Blood dyscrasias or convulsions that do not result in hospitalization
- Development of drug dependency or drug abuse

Clarification regarding Serious Adverse Events

- Death is an outcome of an AE, and not an AE in itself.
- An SAE may occur even if the subject was not on investigational medicinal product at the time of occurrence of the event. Dosing may have been given as treatment cycles or interrupted temporarily before the onset of the SAE.
- “Life-threatening” means that the subject was at immediate risk of death from the event as it occurred. This does not include an event that might have led to death if it had occurred with greater severity.
- Complications that occur during hospitalizations are AEs. If a complication prolongs the hospitalization, it is a SAE.

- “In-patient hospitalization” means the subject is formally admitted to a hospital for medical reasons, for any length of time. This may or may not be overnight. It does not include presentation and care within an emergency department.
- The investigator should attempt to establish a diagnosis of the event on the basis of signs, symptoms and/or other clinical information. In such cases, the diagnosis should be documented as the AE and/or SAE and not the individual signs/symptoms.

Disease Progression and Death Related to Disease Progression:

Given the endpoints of the study, in order to maintain the integrity of the study, the following events that are assessed as unrelated to study drugs will not be considered SAEs:

- Progression of malignancy being studied
- Death due to malignancy being studied

Disease progression and death from disease progression should be reported as SAEs by the investigator only if it is assessed that the study drugs caused or contributed to the disease progression (ie, by a means other than lack of effect). Unrelated disease progression should be captured on the eCRF.

These events will be reported, as appropriate, in the final clinical study report and in any relevant aggregate safety reports.

7.3. Describing Adverse Event Relationship to Study Drug and Study Procedures

The relationship of an AE or SAE to investigational medicinal product should be assessed using clinical judgment, describing the event as either unrelated (No) or related (Yes) consistent with the following definitions:

- **No:** Evidence exists that the AE has an etiology other than the investigational medicinal product. For SAEs, an alternative causality must be provided (eg, pre-existing condition, underlying disease, intercurrent illness, or concomitant medication).
- **Yes:** A temporal relationship exists between the AE onset and administration of the investigational medicinal product that cannot be readily explained by the subject’s clinical state or concomitant therapies. Furthermore, the AE appears with some degree of certainty to be related, based on the known therapeutic and pharmacologic actions or AE profile of the investigational medicinal product. In case of cessation or reduction of the dose the AE may abate or resolve and it may reappear upon rechallenge.

It should be emphasized that ineffective treatment should not be considered as causally related in the context of AE reporting.

The relationship of an AE or SAE to study procedures (eg, invasive procedures such as venipuncture or biopsy) should be assessed using clinical judgment, describing the event as either unrelated (No) or related (Yes) consistent with the following definitions:

- **No:** Evidence exists that the AE has an etiology other than the study procedure.
- **Yes:** A temporal relationship exists between the AE onset and a protocol-mandated procedure that cannot be readily explained by the subject's clinical state or concomitant therapies. Furthermore, the AE appears with some degree of certainty to be related to the study procedure based on the known potential complications of that procedure.

7.4. Adverse Drug Reactions

An adverse drug reaction (ADR) is defined as an AE that is considered causally related to an investigational medicinal product. A serious ADR (SADR) is an ADR which meets the seriousness criteria.

7.5. Unexpected Adverse Event

An unexpected AE is defined as an event that has a nature or severity, or specificity that is not consistent with the applicable Investigator's Brochure or that is symptomatically and pathophysiologically related to a known toxicity but differs because of greater severity or specificity. For example, under this definition, hepatic necrosis would be unexpected (by virtue of greater severity) if the Investigator's Brochure only referred to elevated hepatic enzymes or hepatitis. Similarly, cerebral thromboembolism and cerebral vasculitis would be unexpected (by virtue of greater specificity) if the Investigator's Brochure only listed cerebral vascular accidents. "Unexpected," as used in this definition, refers to an adverse drug experience that has not been previously observed and reported rather than an experience that has not been anticipated based on the pharmacological properties of the study drug.

7.6. Grading of the Severity of an Adverse Event

The severity grading of AEs will be assessed as Grade 1, 2, 3, 4 or 5 using the CTCAE (version 4.03).

For AEs associated with laboratory abnormalities, the event should be graded on the basis of the clinical severity in the context of the underlying conditions; this may or may not be in agreement with the grading of the laboratory abnormality.

The distinction between the seriousness and the severity of an AE should be noted. Severe is a measure of intensity; thus, a severe reaction is not necessarily a serious reaction. For example, a headache may be severe in intensity, but would not be classified as serious unless it met one of the criteria for serious events listed above.

7.7. Special Situation Reports

Special situation reports include pregnancy reports, reports of medication error, abuse, misuse, or overdose, and reports of adverse reactions associated with product complaints.

A pregnancy report is used to report pregnancies following maternal or paternal exposure to the product.

Medication error is any unintentional error in the prescribing, dispensing, or administration of a medicinal product while in the control of the health care provider, subject, or consumer.

Abuse is defined as persistent or sporadic intentional excessive use of a medicinal product by a subject.

Misuse is defined as any intentional or inappropriate use of a medicinal product that is not in accordance with the protocol instructions or the local prescribing information.

An overdose is defined as an accidental or intentional administration of a quantity of a medicinal product given per administration or cumulatively which is above the maximum recommended dose as per protocol or in the product labelling (as it applies to the daily dose of the subject in question).

In cases of a discrepancy in drug accountability, overdose will be established only when it is clear that the subject has taken the excess dose(s) or the investigator has reason to suspect that the subject has taken the additional dose(s).

Product complaint is defined as any written or verbal report arising from potential deviations in the manufacture, packaging or distribution of the product.

Instructions for reporting Special Situation Reports are described in Section [7.8.1](#)

7.8. Investigator Requirements and Instructions for Reporting Adverse Events and Serious Adverse Events to Gilead

All SAEs, regardless of cause or relationship, that occur after the subject first consents to participate in the study (ie, signing the informed consent) and throughout the duration of the study, including the protocol-required post treatment follow-up period, must be reported to the CRF/eCRF database and Gilead Drug Safety and Public Health (DSPH) as instructed. This also includes any SAEs resulting from protocol-associated procedures performed from screening onwards.

All AEs, regardless of cause or relationship, that occur from initiation of study medication until 4 weeks after last administration of study IMP must be reported to the CRF/eCRF database as instructed.

Any SAEs and deaths that occur after the post treatment follow-up visit but within 30 days of the last dose of study IMP, regardless of causality, should also be reported.

All AEs should be followed up until resolution if possible. If by the last day on study (including the off-study medication follow-up period) the AE has not resolved, then the AE will be followed up until the investigator and/or Gilead Sciences determine that the subject's condition is stable. However, Gilead Sciences may request that certain AEs be followed until resolution.

Investigators are not obligated to actively seek SAEs after the period. However, if the investigator learns of any SAEs that occur after study participation has concluded and the event is deemed relevant to the use of IMP, he/she should promptly document and report the event to Gilead DSPH.

- All AEs and SAEs will be recorded in the CRF/eCRF database within the timelines outlined in the CRF/eCRF completion guideline.
- At the time of study start, SAEs will be reported using a paper serious adverse event reporting form. During the study conduct, sites may transition to an electronic SAE (eSAE) system. Gilead will notify sites in writing and provide training and account information prior to implementing an eSAE system.

Serious Adverse Event Paper Reporting Process

- All SAEs will be recorded on the serious adverse event report form and submitted by faxing the report form within 24 hours of the investigator's knowledge of the event to the attention of Gilead DSPH or to the designated CRO.

Electronic Serious Adverse Event (eSAE) Reporting Process

- Site personnel record all SAE data in the eCRF database and from there transmit the SAE information to Gilead DSPH within 24 hours of the investigator's knowledge of the event. Detailed instructions can be found in the eCRF completion guidelines.
- If for any reason it is not possible to record the SAE information electronically, ie, the eCRF database is not functioning, record the SAE on the paper serious adverse event reporting form and submit within 24 hours as described above.
- As soon as it is possible to do so, any SAE reported via paper must be transcribed into the eCRF Database according to instructions in the eCRF completion guidelines.
- If an SAE has been reported via a paper form because the eCRF database has been locked, no further action is necessary.
- All AEs and SAEs will be recorded in the CRF/eCRF database within the timelines outlined in the CRF/eCRF completion guideline.
- Site personnel record all SAE data in the eCRF database and from there transmit the SAE information to Gilead DSPH within 24 hours of the investigator's knowledge of the event. Detailed instructions can be found in the eCRF completion guidelines.

- If for any reason it is not possible to record the SAE information electronically, ie, the eCRF database is not functioning, record the SAE on the paper serious adverse event reporting form and submit within 24 hours as described above.
- As soon as it is possible to do so, any SAE reported via paper must be transcribed into the eCRF Database according to instructions in the eCRF completion guidelines.
- If an SAE has been reported via a paper form because the eCRF database has been locked, no further action is necessary.
- For fatal or life-threatening events, copies of hospital case reports, autopsy reports, and other documents are also to be submitted by e-mail or fax when requested and applicable. Transmission of such documents should occur without personal subject identification, maintaining the traceability of a document to the subject identifiers.
- Additional information may be requested to ensure the timely completion of accurate safety reports.

Any medications necessary for treatment of the SAE must be recorded onto the concomitant medication section of the subject's CRF/eCRF and the event description section of the SAE form.

Site reporting requirements for AEs are summarized in [Table 7-1](#).

Table 7-1. Site Reporting Requirements for Adverse Events

Classification	Reporting Time	Reporting Action
Serious	Within 24 hours	Record and submit all SAE information on appropriate eCRFs and from there transmit the SAE information to Gilead Sciences DSPH. Print out the SAE report in order to submit to the site IRB/IEC, as per local IRB/IEC requirements. Detailed instructions can be found in the eCRF completion guidelines.
	Per eCRF submission procedure	Record and submit information on appropriate eCRFs
Nonserious	Per eCRF submission procedure	Record and submit information on appropriate eCRFs

Contact details for PPD Pharmacovigilance are provided in [Table 7-2](#):

Table 7-2. Contact Information for Reporting Serious Adverse Events

PPD Pharmacovigilance:	Fax: PPD SAE phone: PPD
------------------------	----------------------------

Report an SAE to PPD Pharmacovigilance if eSAE reporting is unavailable. Also report Special Situations and Pregnancies to PPD Pharmacovigilance per below (Section [7.8.1](#)).

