6.8. Immediate Post-Treatment Safety Follow-up

After the last dose of study drug, subjects should be followed for any drug-related AEs and/or ongoing serious adverse events (SAEs) until those events have resolved or become stable, whichever occurs later. The site will contact the study subject regardless of AE/SAE status or initiation of new anti-tumor regimen 30 (\pm 7) days following completion of the subject's last dose of study drug to assess for AEs. Subjects will specifically be asked about the development of any adverse events since stopping the study. Contact the subject by phone (or in person, if necessary) to assess the subject's condition and record any adverse events reported during the follow-up contact. Document the phone call or visit.

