7.8.3. Post-Study Reporting Requirements

All AEs and SAEs including deaths, regardless of cause or relationship, must be reported for subjects on study through the last study visit and the 30-day follow-up phone call (or in person, if necessary).

Any SAEs and deaths that occur after the End of Study visit but within 30 days of the last dose of investigational medicinal product, regardless of causality, should also be reported.

Investigators are not obligated to actively seek SAEs after the 30 day time period. However, if the investigator learns of any SAEs that occur after study participation and the event is deemed relevant to the use of investigational medicinal products, he/she should promptly document and report the event to Gilead Sciences DSPH.

7.9. Clinical Laboratory Abnormalities and Other Abnormal Assessments as Adverse Events or Serious Adverse Events

Laboratory abnormalities are usually not recorded as AEs or SAEs. However, laboratory abnormalities (eg, clinical chemistry, hematology, and urinalysis) that require medical or surgical intervention or lead to investigational medicinal product interruption or discontinuation must be recorded as an AE, as well as an SAE, if applicable. In addition, laboratory or other abnormal assessments (eg, electrocardiogram, X-rays, vital signs) that are associated with signs and/or symptoms must be recorded as an AE or SAE if they meet the definition of an AE or SAE as described in Sections 7.1 and 7.3, respectively. If the laboratory abnormality is part of a syndrome, record the syndrome or diagnosis (ie, anemia) not the laboratory result (ie, decreased hemoglobin).

Severity should be recorded and graded according to the CTCAE (version 4.03).

For AEs associated with laboratory abnormalities, the event should be graded on the basis of the clinical severity in the context of the underlying conditions; this may or may not be in agreement with the grading of the laboratory abnormality.

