8.5.3.3. Adverse Events

All AEs will be listed. The focus of AE summarization will be on treatment-emergent AEs. A treatment-emergent AE is defined as an AE that occurs or worsens in the period from the first dose of study treatment to 30 days after the last dose of study treatment. Adverse events that occur before the first dose of study treatment or > 30 days after the subject is discontinued from study treatment will be included in data listings.

Adverse events will be classified using the Medical Dictionary for Regulatory Activities (MedDRA) (<http://www.meddramsso.com>) with descriptions by System Organ Class, High-Level Group Term, High-Level Term, Preferred Term, and Lower-Level Term. The severity of AEs will be graded by the investigator according to the CTCAE, Version 4.03 whenever possible. If a CTCAE criterion does not exist for a specific type of AE, the grade corresponding to the appropriate adjective will be used by the investigator to describe the maximum intensity of the AE: Grade 1 (mild), Grade 2 (moderate), Grade 3 (severe), Grade 4 (life threatening), or Grade 5 (fatal). The relationship of the AE to the study drug will be categorized as related or unrelated.

Treatment-emergent AEs will be summarized. Summary tables will be presented to show the number of subjects reporting treatment-emergent AEs by severity grade and corresponding percentages. A subject who reports multiple treatment-emergent AEs within the same Preferred Term (or System Organ Class) is counted only once for that Preferred Term (or System Organ Class) using the worst severity grade. Adverse event descriptions will be presented in alphabetical order of System Organ Class, then by decreasing frequency in the “overall” column for a given Preferred Term.

Separate listings and summaries will be prepared for the following types of treatment-emergent AEs:

- Study-drug-related AEs
- AEs that are Grade ≥ 3 in severity
- AEs leading to study drug interruption and/or dose modification
- AEs leading to study drug discontinuation
- SAEs (with categorization of the primary reason that the AE is considered serious, eg, death, hospitalization, etc)

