#### **7.1.5. Treatment-Emergent Adverse Events**

##### **7.1.5.1. Definition of Treatment-Emergent Adverse Events**

Treatment-emergent adverse events (TEAEs) are defined as 1 or both of the following:

- Any AEs with an onset date on or after the study drug start date and no later than 30 days after permanent discontinuation of study drug

- Any AEs leading to premature discontinuation of study drug.

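### For non-serious AEs the protocol gives conflicting collection periods, and the closing contact may come on Day 23, so collection through the 30-day treatment-emergent window is not assured.

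*Protocol*

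**What the plan says.** Collection rules for AEs in the protocol:

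- Section 7.8: all AEs "that occur from initiation of study medication until 4 weeks after last administration of study IMP must be reported to the CRF/eCRF database as instructed".
- Section 7.1: AEs include "All AEs that occur from the signing of the informed consent onwards and throughout the duration of the study, including the 30-day follow-up off-study period".
- Section 7.8.3: all AEs and SAEs "must be reported for subjects on study through the last study visit and the 30-day follow-up phone call".
- Sections 6.8 and 6.9.6 and Appendix 2 note f (repeated in SAP Appendix 1 note f): the site contacts the subject 30 (±7) "days following completion of the subject's last dose of study drug to assess for AEs".
- Sections 7.8 and 7.8.3 each add that SAEs and deaths within 30 days of the last dose must be reported, whatever their cause, even if they follow the last planned visit. Neither section has a matching sentence for non-serious AEs.

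Analysis windows:

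- Protocol 8.5.3.3: an AE is treatment-emergent if it occurs or worsens "in the period from the first dose of study treatment to 30 days after the last dose of study treatment".
- SAP 7.1.5.1: onset on or after the first dose and "no later than 30 days after permanent discontinuation of study drug", plus any AE that leads to premature discontinuation.

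**The concern.** The safety tables rest on a 30-day off-drug window. The collection rules should fill that window in the same way at every site, and as written they need not. One section stops required reporting two days short of it. Another ties the end of reporting to a call that may be made a week before it closes. How much of the window is covered then depends on which section a site follows and on the day it calls, and the tables would not show the difference.

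The exposed events are not only trivial ones. Protocol 7.6 notes that a severe event need not be serious. A non-serious Grade 3 event therefore falls in the exposed group, and SAP 7.1.6.1 tabulates treatment-emergent AEs of Grade 3 or higher separately. Safety and tolerability is a secondary objective of the trial.

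The start of collection also differs: consent in 6.2.1, 7.1 and Appendix 2 note f, but first dose in 7.8.

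**Working it through.** This is day arithmetic. The last dose is Day 0, and the plan states no figure of its own to reproduce.

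**Inputs**

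- Analysis window: Day 30 (Protocol 8.5.3.3, SAP 7.1.5.1).
- Reporting limit in 7.8: 4 × 7 = Day 28.
- Contact window in 6.8: 30 − 7 = Day 23 to 30 + 7 = Day 37.

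**Gap under the 7.8 rule.** 30 − 28 = 2 days (Days 29-30). 2/30 = 6.7% of the off-drug window.

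**Gap after an early contact.** A call on Day d < 30 leaves 30 − d days unqueried. At d = 23 this is 7 days (Days 24-30), and 7/30 = 23.3%. At d ≥ 30 it is 0.

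**How often the contact can be early.** Days 23-37 give 15 permitted days, of which 7 (Days 23-29) fall before Day 30. If contacts were spread evenly over the window (an assumption), the mean shortfall would be (7 + 6 + 5 + 4 + 3 + 2 + 1)/15 = 28/15 = 1.9 days.

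**SAEs and deaths.** Reporting is required to Day 30, so the gap is 30 − 30 = 0 days.

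**Share of the whole treatment-emergent window.** That window also includes all time on drug, which the documents do not fix. Assumed durations:

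| Time on drug (assumed) | Window, days | 2-day gap | 7-day gap |
|---|---|---|---|
| 8 weeks | 56 + 30 = 86 | 2.3% | 8.1% |
| 16 weeks | 112 + 30 = 142 | 1.4% | 4.9% |
| 24 weeks | 168 + 30 = 198 | 1.0% | 3.5% |

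**Whether another visit closes the gap.** In Appendix 2 the AE row is marked at the progression or end-of-study visit and at the 30-day follow-up, but not at tumor response assessments. Disease follow-up after stopping drug therefore schedules no AE query. The end-of-study visit does record AEs, but Section 6.7 does not fix it after the call. It could fall in Days 24-30 by chance, not by plan.

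**Start of collection.** Screening may last up to 35 days (6.2.1). AEs in that period are collected under 7.1 but are not required under 7.8 unless serious. Treatment-emergent AEs start at first dose in both documents, so this conflict reaches the AE listings and not the treatment-emergent tables.

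**The case against.** The best reply is that 7.8 is one sentence in a protocol that elsewhere describes a 30-day follow-up for all AEs. Section 7.8 says what must be reported and does not bar later entries. A site that reads 7.1 and 7.8.3 together and calls on Day 30 or later collects the whole window. Many subjects also remain in contact after stopping drug, through imaging, hematology and follow-up of unresolved drug-related events. As a share of the full treatment-emergent window the gap is a few percent, and 23.3% is the single worst permitted day.

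Most of this stands. It makes the shortfall a risk, not a certainty, and keeps it small. It does not remove the conflict. Section 7.8.3 ends AE reporting at the last visit and the call, and the call may be made on Day 23. Both 7.8 and 7.8.3 recognise that planned follow-up can end before Day 30, since they extend SAEs and deaths past it, but they do not extend non-serious AEs.

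A reader might go further in three ways that the documents do not support:

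- **That SAE and 30-day death summaries are also incomplete.** Reporting of both is required to Day 30 without condition, and 7.8.3 lifts the duty to seek SAEs actively only after 30 days.
- **That AE reporting as a whole closes at 4 weeks.** Sections 7.1 and 7.8.3 say otherwise. The protocol contradicts itself and does not set one short cut-off.
- **That the hepatic cases in Section 1.5.4 show what would be missed.** Those events began 1 and 7 days after the last dose, and the one stated peak came about a week after a Day 1 onset. All of this falls well before Day 23.

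**Conclusion.** The inconsistency is real and limited to non-serious AEs. A site can comply with a written rule of the protocol and still leave 2 days (under 7.8) to 7 days (after a Day 23 call) of the 30-day off-drug window without required or queried reporting. Whether this happens depends on the section a site follows and on its contact day, and neither can be known from the documents. The percentages of the full window rest on assumed treatment durations of 8 to 24 weeks, and the 1.9-day mean on evenly spread contacts.

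SAE and death reporting, efficacy, sample size and error rates are untouched. The start-date conflict affects listings only. The point is worth correcting because the affected tables include Grade 3 or higher events and the correction is simple.

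**What to change.** 1. In Protocol 7.8, require all AEs from signing of informed consent until 30 days after the last dose.
2. State the same Day 30 end point in 7.1 and 7.8.3, so that the study duration and the last visit do not remain as competing end points.
3. In 6.8, 6.9.6 and Appendix 2 note f, and in SAP Appendix 1 note f, change the contact to 30 (+7) days. Alternatively, keep ±7 and state that non-serious AEs through Day 30 must still be collected when the contact is earlier.

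The cost is amendment wording. With the +7 option no call is added, but some calls move up to 7 days later. Keeping ±7 would mean a second enquiry after an early call. Either change helps only subjects whose contact is still to come.
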